10.5 Efficacy Endpoints

Efficacy endpoints include:

1. Device success (VARC-2)
2. Cardiovascular and heart failure hospitalizations at 30 days and 6 months
3. Heart failure events at 30 days and 6 months
4. Hemodynamic performance metrics by Doppler echocardiography at discharge, 30 days, and 6 months
 - Mean aortic gradient

- Effective orifice area
 - Degree of total, para, and transvalvular prosthetic regurgitation
 - Incidence of moderate and severe patient-prosthesis mismatch (PPM)
5. Change from baseline in New York Heart Association (NYHA) functional classification at 30 days and 6 months
 6. Change in six-minute walk test (6MWT) from baseline at 6 months
 7. Change in Kansas City Cardiomyopathy (KCCQ) from baseline at 30 days and 6 months
 8. Change in left ventricular ejection fraction (LVEF) from baseline at 6 months
 9. Change in peak global longitudinal strain (GLS) from baseline at 6 months
 10. Change in left ventricular filling pressure (E:e') from baseline at 6 months
 11. Change in stroke volume index (SVI) from baseline at 6 months
 12. Change in NT-pro B-type natriuretic peptide (NT-proBNP) from baseline at 6 months

Analyses of the efficacy endpoints will be descriptive. The attempted implant set will be used for safety and quality of life outcomes. However, the efficacy endpoints involving echocardiographic variables will be analyzed for the implanted set. Continuous variables will be summarized as the number of subjects, mean, standard deviation, median, first and third quartiles, minimums, and maximums. Categorical variables will be summarized as counts and percentages. For each time-related event, Kaplan-Meier rates (cumulative incidence) and 95% two-sided confidence intervals will be calculated. Efficacy endpoints involving echocardiographic variables will be based on ECL reported data.

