The primary objectives of this feasibility study are as follows:

1. Characterize the spectrum of cardiac function, symptomology, and severity of aortic stenosis in the study populations,
2. Estimate event rates for potential safety and effectiveness endpoints to be evaluated in pivotal studies for the proposed patient populations, and
3. Evaluate the effect of TAVR on cardiac function, functional capacity, effort tolerance, and patient-reported quality of life in the study populations.

The study objectives and associated endpoints are intended to fully characterize the spectrum of aortic stenosis (AS) severity, left ventricular (LV) function, and symptomology of patients with moderate

symptomatic and severe asymptomatic AS, provide information on event rates for pivotal sample size estimations, and refine the entrance criteria for future pivotal studies. The full list of protocol defined endpoints are detailed in Section 7.9. Of the protocol defined endpoints, the following key study endpoints have been identified:

Key Safety Endpoints:

- All-cause mortality at 30 days and 6 months
- All stroke (disabling and non-disabling) at 30 days and 6 months
- Valve-related dysfunction requiring repeat procedure at 30 days and 6 months
- New permanent pacemaker implant (PPI) at 30 days and 6 months

Key Efficacy Endpoints:

- Cardiovascular and heart failure hospitalizations at 30 days and 6 months
- Heart failure events at 30 days and 6 months
- Change in Kansas City Cardiomyopathy Questionnaire (KCCQ) at 6 months
- Change in Six-Minute Walk Test (6MWT) at 6 months
- Change in cardiac function by echo (LVEF, Peak GLS, E:e') at 6 months

5. Investigation Plan

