7.2 General Methodology

Continuous variables will be summarized descriptively with number of observations, mean, standard deviations, median, first and third quartiles, minimums and maximums. Categorical data will be presented as counts and percentages.

For time-to-event outcomes using Kaplan-Meier methods, the time points of 30 days, 6 months, 1 year, 2 years, 3 years, 4 years, and 5 years will correspond to 30, 183, 365, 730, 1095, 1460, and 1825 days post-implant, respectively. For each applicable time point, the event or event-free rate, the number of subjects at risk, the number of subjects with an event, the Greenwood standard error of the estimate, and the log-log transformed 95% confidence interval using the Greenwood standard error will be reported. For subjects with an event, the date of event will be based on the first event occurrence. For subjects without an event, date of censoring will be based on the latest of all follow-up visits, assessments, and events (for non-death events).

All statistical analyses will be performed using SAS version 9.4 or higher (SAS Institute, Cary, North Carolina, USA) or other widely accepted statistical or graphical software.

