7.9.2 Efficacy Endpoints

7.9.2.1 Device success (VARC-2)

Device success is defined as meeting all of the following:

- Absence of procedural mortality, AND
- Correct positioning of a single prosthetic heart valve into the proper anatomical location, AND
- Absence of patient prosthesis-mismatch AND mean aortic valve gradient < 20 mmHg (or peak velocity < 3 m/sec), AND
- Absence of moderate or severe prosthetic valve regurgitation.

Components of device success will be reported on the procedure CRF, the echo core lab CRF at discharge, and CEC CRF:

- Procedural mortality will be defined as any death occurring within 30 days of implant or prior to hospital discharge.
- Correct positioning of the single prosthetic heart valve into the proper anatomical location will be reported by the investigator on the procedure CRF.
- Absence of patient-prosthesis mismatch will be derived from the echo core lab data at discharge. Patient prosthesis mismatch is defined in Section 7.9.2.4.
- Mean aortic valve gradient < 20 mmHg (or peak velocity < 3 m/sec) will be derived from the echo core lab CRF at discharge
- Absence of moderate or severe prosthetic valve regurgitation will be derived from the echo core lab CRF at discharge

The endpoint will be reported as the count and percentage of subjects achieving device success with two-sided 95% exact binomial confidence interval. Subjects will be defined as success if all components are met. Subjects will be defined as failure if any one component with available data is not met, regardless if data are available for all components. Subjects missing data for any components and not meeting criteria for failure will be considered to have a missing outcome. The numerator will include the number of subjects with device success and the denominator will include subjects evaluable for device success (known status of success or failure). The components of device success will also be summarized descriptively. The endpoint will be analyzed using the Implanted set.

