7.9.2.3 Heart failure events at 30 days and 6 months

Heart failure events will be adjudicated by the CEC and analysis will be based on data collected on the CEC adjudication form. The endpoint will be analyzed with Kaplan-Meier survival analysis according to Section 7.2 for each time point. The primary analysis will use the Attempted Implant set.

7.9.2.4 Hemodynamic performance metrics by Doppler echocardiography at discharge, 30 days, and 6 months

The following hemodynamic performance metrics by Doppler echocardiography will be reported at discharge, 30 days, and 6 months:

- Mean aortic gradient
- Effective orifice area
- Degree of total, para, and transvalvular prosthetic regurgitation
- Incidence of moderate and severe patient-prosthesis mismatch (PPM)

Endpoint Definitions:

Mean aortic gradient will be reported in units of mmHg.

Effective Orifice Area (EOA) in cm² will be derived according to the following formula

$$EOA = LVOT\ diameter^2 \times 0.785 \times (LVOT\ VTI / Aortic\ valve\ VTI)$$

Where: LVOT VTI is the velocity time integral of the left ventricular outflow tract in cm, and aortic valve VTI is the velocity time integral of the aortic prosthesis in cm.

Degree of total, para, and transvalvular prosthetic regurgitation will be reported in categories of none, trace, mild, moderate, and severe.

Patient-prosthesis mismatch (PPM)⁽¹⁾ is defined as follows:

For subjects with body mass index (BMI) < 30 kg/cm²

- **Moderate PPM:** EOAI = 0.85 – 0.65
- **Severe PPM:** EOAI < 0.65

For subjects with BMI ≥ 30 kg/cm²

- **Moderate PPM:** EOAI = 0.70 – 0.60
- **Severe PPM:** EOAI < 0.60.

Note that in the above, Effective Orifice Area Index (EOAI) in cm²/m² is defined as EOAI = EOA/BSA where EOA is the effective orifice area in cm² and BSA is the body surface area in m².

Analysis Methods:

Data for all endpoints will be reported on the core lab echo CRF. Mean aortic gradient and EOA will be summarized descriptively as continuous outcomes at each time point. Change from baseline in mean aortic gradient and EOA will also be summarized descriptively along with two-sided 95% confidence interval and p-value from a paired t-test. The degree of total, para, and transvalvular prosthetic regurgitation and incidence of moderate and severe PPM will be summarized with frequency counts and percentages at each follow-up time point. Analysis of each hemodynamic performance outcome will use the Implanted set.

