7.9.3 Additional Outcome Measures

The following outcome measures will be also be evaluated:

1. All-cause and cardiovascular mortality annually through 5 years
2. All stroke (disabling and non-disabling) annually through 5 years
3. Cardiovascular and heart failure hospitalizations annually through 5 years
4. Heart failure events annually through 5 years
5. New York Heart Association (NYHA) functional classification at 30 days, 6 months, and annually through 5 years
6. Change in New York Heart Association (NYHA) functional classification from baseline annually through 5 years
7. Kansas City Cardiomyopathy (KCCQ) annually through 5 years
8. Hemodynamic performance metrics by Doppler echocardiography
 - Mean aortic gradient annually through 5 years
 - Effective orifice area annually through 5 years
 - Degree of total, para, and transvalvular prosthetic regurgitation annually through 5 years
 - Incidence of moderate and severe patient-prosthesis mismatch (PPM) annually through 5 years
9. Prosthetic valve thrombosis 30 days, 6 months, and annually through 5 years
10. Prosthetic valve endocarditis at 30 days, 6 months, and annually through 5 years
11. Bioprosthetic valve dysfunction (BVD) at 30 days, 6 months, and annually through 5 years
12. Bioprosthetic valve failure (BVF) at 30 days, 6 months, and annually through 5 years
13. Valve-related dysfunction requiring repeat procedure annually through 5 years

Additional Outcomes Measures 1-10 and 13:

Analysis for additional outcome measures 1-8 and 13 will follow the analysis methods defined for the same safety and efficacy endpoints at earlier timepoints described in Section 7.9.1 and 7.9.2, respectively. Prosthetic valve thrombosis and prosthetic valve endocarditis, additional outcome measures 9 and 10, will be analyzed with Kaplan-Meier analysis as described in Section 7.2. The analysis

of additional outcome measures 9 and 10 will be based on CEC adjudications using the Attempted Implant set.

Additional Outcome Measure 11 - Bioprosthetic valve dysfunction (BVD)⁽¹⁾ at 30 days, 6 months, 1 year:

Bioprosthetic valve dysfunction (BVD) is defined as meeting any of the following:

- Moderate or severe stenosis defined as any of the following:
 - Peak aortic velocity > 4 m/s OR mean aortic gradient > 40 mmHg, AND EOA < 0.8 cm²
 - Peak aortic velocity > 4 m/s OR mean aortic gradient > 40 mmHg, AND EOA ≥ 0.8 cm², AND DVI < 0.25

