 - Peak aortic velocity ≤ 4 m/s and mean aortic gradient ≤ 40 mmHg, AND EOA < 0.8 cm², AND DVI < 0.25

Note: In the above, for subjects with BSA < 1.6 m², the EOA criteria for significant (moderate or severe) stenosis is < 0.6 cm². Additionally, for subjects with LVOT diameter > 2.5 cm, the DVI criteria for significant (moderate or severe) stenosis is < 0.2.

- Moderate or severe paravalvular regurgitation
- Moderate or severe transvalvular regurgitation
- Moderate or severe total regurgitation

Analysis of BVD will be based on data collected on the core lab CRF. The numerator for each time point will include the number of subjects meeting any of the components of BVD. The denominator will include any subject with BVD and subjects with no evidence of BVD having evaluable data for all 4 components. BVD will be summarized with frequency counts and percentages. The components of BVD will also be summarized. The analysis will be performed using the Implanted set.

Additional Outcome Measure 12 - Bioprosthetic valve failure (BVF)⁽²⁾ at 30 days, 6 months, 1 year

Bioprosthetic valve failure (BVF) is defined as meeting any of the following:

- Autopsy findings of bioprosthetic valve dysfunction, likely related to the cause of death, or valve-related death (i.e. any death caused by bioprosthetic valve dysfunction or sudden unexplained death following diagnosis of bioprosthetic valve dysfunction)
- Repeat intervention (i.e. valve-in-valve TAVI, paravalvular leak closure or SAVR following confirmed diagnosis of bioprosthetic valve dysfunction)
- Severe bioprosthetic valve dysfunction

A Kaplan-Meier analysis as described in Section 7.2 will be performed for BVF at 30 days, 6 months, and annually through 5 years. The analysis will use the Implanted set.

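### Patient-prosthesis mismatch, prosthetic regurgitation and bioprosthetic valve dysfunction rates are reported without a confidence interval, although device success gets an exact one

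*SAP*

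**What the plan says.** SAP 7.9.2.4 covers the Doppler echocardiography endpoints at discharge, 30 days and 6 months. For the categorical ones it states that "incidence of moderate and severe PPM will be summarized with frequency counts and percentages at each follow-up time point"; the same sentence applies this to the degree of regurgitation. Regurgitation is recorded in five grades from none to severe. Mismatch (PPM) is classed as moderate or severe from the indexed orifice area.

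SAP 7.9.3 extends this to the yearly visits. Measure 8, the annual hemodynamic metrics, inherits the earlier method: "Analysis for additional outcome measures 1-8 and 13 will follow the analysis methods defined for the same safety and efficacy endpoints at earlier timepoints". For measure 11, "BVD will be summarized with frequency counts and percentages".

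No general rule adds an interval. SAP 7.2 says "Categorical data will be presented as counts and percentages", and protocol 10.5 says "Categorical variables will be summarized as counts and percentages". Protocol 10.6 matches 10.5, and both name confidence intervals only for time-related events.

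Elsewhere the SAP does pre-specify 95% intervals:
- Kaplan-Meier endpoints: log-log limits with Greenwood standard errors (7.2).
- Continuous changes from baseline, including mean gradient and effective orifice area within 7.9.2.4 itself: limits reported with a paired t-test.
- Device success: a "two-sided 95% exact binomial confidence interval" (7.9.2.1).

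**The concern.** The second primary objective is to "Estimate event rates for potential safety and effectiveness endpoints to be evaluated in pivotal studies for the proposed patient populations", and SAP section 4 adds that the rates should inform pivotal sample-size work. An estimated rate from at most 75 implanted subjects is of limited use for planning without a statement of its precision. The sample size was not set by statistical methods (SAP section 6), so no precision target elsewhere fills that role.

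The treatment is also uneven. Absence of PPM and absence of moderate or severe regurgitation at discharge are components of device success. The composite gets an exact interval; its components are only summarised descriptively, and the same measures at 30 days, 6 months and each year get counts and percentages. The study's descriptive character does not explain this, since device success is equally descriptive.

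At stake is how the tables are read. A low observed percentage from 50 to 75 subjects can look firmer than it is, and the interval shows which true rates the data leave open.

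**Working it through.** The plan gives no precision or power figure for these rates, so there is none to reproduce.

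**Inputs**
- Maximum n: 75 implanted (SAP 5.1).
- Initial analysis: 50 to 75 subjects with 6-month follow-up, possibly earlier if enrollment is slow (SAP 7.8).
- Missing data are not imputed (SAP 7.4), so evaluable numbers may fall below 75. I use 60 as an assumed intermediate value.
- Expected rates of PPM, regurgitation or BVD: not given. The event counts below are assumptions.

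**Method.** Two-sided 95% exact binomial (Clopper-Pearson) limits, the type SAP 7.9.2.1 specifies for device success. For x events in n subjects:
- lower limit = 2.5% quantile of Beta(x, n − x + 1), or 0 if x = 0
- upper limit = 97.5% quantile of Beta(x + 1, n − x)

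For x = 0 the upper limit reduces to 1 − 0.025^(1/n):
- n = 75: 1 − 0.025^(1/75) = 4.8%
- n = 60: 1 − 0.025^(1/60) = 6.0%
- n = 50: 1 − 0.025^(1/50) = 7.1%

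| Assumed count | Observed rate | Exact 95% interval |
|---|---|---|
| 0/75 | 0% | 0 to 4.8% |
| 1/75 | 1.3% | 0.03 to 7.2% |
| 3/75 | 4.0% | 0.83 to 11.25% |
| 10/75 | 13.3% | 6.6 to 23.2% |
| 0/60 | 0% | 0 to 6.0% |
| 0/50 | 0% | 0 to 7.1% |
| 2/50 | 4.0% | 0.49 to 13.71% |

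At 3/75 the upper limit is about 13.5 times the lower (11.25 / 0.83). At 10/75 the interval still spans 16.6 percentage points (23.2 − 6.6), so the point does not depend on the events being rare.

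**Chance of seeing no events**, (1 − p)^n:
- true rate 2%: 0.98^75 = 0.22; 0.98^50 = 0.36
- true rate 3%: 0.97^75 = 0.10; 0.97^50 = 0.22

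**The case against.** Several points on the other side stand, and they limit the weight of this one.

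- **The percentages do not stand alone.** Counts are reported with them, SAP 7.4 requires the number analysed each time, and 7.9.3 defines the BVD denominator. Anyone planning a pivotal study can compute the exact interval. The same is true of device success, however, where the SAP chose to pre-specify one.
- **These are not key endpoints.** The key list in SAP section 4 omits PPM, regurgitation and BVD. The key event rates on that list all have Kaplan-Meier intervals. No passage says that the echo rates will drive a pivotal sample size; the objective speaks only of potential endpoints.
- **Some serious valve outcomes are already covered.** Bioprosthetic valve failure, which includes severe BVD, and valve dysfunction leading to a repeat procedure both have Kaplan-Meier intervals.
- **Regurgitation is a five-grade variable.** A frequency table is its natural summary. An interval requires a dichotomy that 7.9.2.4 does not set out, although device success and BVD already use moderate or severe as the cut.
- **Counts and percentages are the general rule for categorical data.** They also apply to NYHA class, and device success is the exception. The SAP and protocol agree, so the documents do not support reading this as a conflict between them or as selective withholding.

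A reader might also infer that yearly shifts of one or two subjects would be mistaken for a trend and that intervals would prevent it. The documents plan no trend analysis. The same subjects are measured repeatedly, so separate intervals at each visit would not assess change between years.

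**Conclusion.** The omission is real: no section gives PPM, prosthetic regurgitation or BVD rates an interval, and the method already chosen for device success would supply one. With 50 to 75 subjects the unreported uncertainty is material. An observed 0% leaves open a true rate of up to 4.8% at n = 75 or 7.1% at n = 50, and an observed 13.3% at n = 75 leaves open 6.6 to 23.2%.

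These sizes rest on assumed counts and on full evaluability at the stated n. A reader might infer that the study will report a zero or near-zero rate that then enters pivotal planning unqualified. The documents do not support that: they give no expected rates, do not say which rates will be used for planning, and do report the counts needed to judge precision. The gap biases no estimate and leaves the sample size unaffected. It is a cheap improvement in reporting.

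**What to change.** In SAP 7.9.2.4 and in 7.9.3 (measures 8 and 11), keep the frequency tables. At each time point, add two-sided 95% exact binomial intervals by the method of SAP 7.9.2.1, with the evaluable denominator shown, for:
- moderate PPM, severe PPM, and the two combined;
- regurgitation dichotomised as moderate or severe versus less, separately for total, paravalvular and transvalvular;
- BVD.

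No protocol amendment is needed. The SAP already adds an exact interval for device success that protocol 10.5 does not mention. Editing the protocol would start the process in its section 12.6: submission to affected regulators, ethics approvals and investigator signatures.

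The cost is SAP wording and a few extra table columns. The downside is that the reported rates will look less certain. Endpoints, data collection and sample size stay as they are.

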Information and definitions for ACCF/AHA Heart Failure stages⁶⁴, NYHA functional classifications, and Modified Rankin Score⁶⁵ are provided in Table 14, Figure 6, Table 15, and Table 16.

Table 14. ACCF/AHA heart failure stages

Stage	Description
A	At high risk for HF but without structural heart disease or symptoms of HF
B	Structural heart disease but without signs or symptoms of HF
C	Structural heart disease with prior or current symptoms of HF
D	Refractory HF requiring specialized interventions

[figure not shown]

Figure 6. Stages in the development of heart failure. Adapted from Hunt et al.⁶⁴

Table 15. NYHA classification

Class	Description
Class I	Patient is without limitations of physical activity. Ordinary physical activity does not cause undue fatigue, palpitations, or dyspnea.
Class II	Patient has slight limitations of physical activity. Is comfortable at rest. Ordinary physical activity results in fatigue, palpitations, or dyspnea.
Class III	Patient has marked limitations of physical activity. Is comfortable at rest. Less than ordinary activity causes fatigue, palpitations, or dyspnea.
Class IV	Patient has inability to carry on any physical activity without discomfort. Heart failure symptoms are present even at rest or with minimal exertion.

Table 16. Modified Rankin score

Score	Description
0	No symptoms at all
1	No significant disability despite symptoms; able to carry out all usual duties and activities
2	Slight disability; unable to carry out all previous activities, but able to look after own affairs without assistance
3	Moderate disability; requiring some help, but able to walk without assistance
4	Moderately severe disability; unable to walk without assistance and unable to attend to own bodily needs without assistance
5	Severe disability; bedridden, incontinent and requiring constant nursing care and attention
6	Dead

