7.4 Handling of Missing, Unused, and Spurious Data and Dropouts

Every effort will be undertaken to minimize missing data. Missing (accidentally, due to withdrawal, missing follow-up or loss to follow-up, etc.), unused and spurious data will remain identifiable in the database. For time-to-event outcomes, dropouts will be censored at the time of discontinuation, consistent with the Kaplan-Meier approach. Unless otherwise specified, all analyses will be based on available data and missing data will not be imputed. The number of subjects included in each analysis will be reported so that the reader can assess the potential impact of missing data.

In the case of partial dates, unknown portions will be imputed for the purposes of analysis. If only the month and year are known, the event or assessment will be analyzed as if it occurred on the 15th of the known month. If only the year is known, the event or assessment will be analyzed as if it occurred on June 30th of the known year. Imputation of partial dates is subject to the restriction that pre-implant events must occur between the date of informed consent and the date of implant and post-implant events must occur after the date of implant.

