7.8 Interim Analyses

An initial analysis is planned when the first 50 to 75 implanted subjects have completed his/her 6 month follow-up; however initial analyses may be performed earlier if enrollment is slower than expected. Initial analyses will assess all safety and efficacy endpoints based on available data. The analysis will be descriptive and no formal interim analyses are planned for the purpose of early stopping or sample size re-estimation.

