7.9.2.5 Change from baseline in New York Heart Association (NYHA) functional classification at 30 days and 6 months

New York Heart Association (NYHA) functional classification will be reported on the follow-up CRF by the investigator as Class I, II, III, or IV. NYHA class will be summarized with frequency counts and

percentages for each follow-up time point. At each follow-up time point, change in NYHA class from baseline will be reported descriptively both as categorical and continuous variable. Categorical summary of change will include a summary of subjects with change of 3, 2, 1, 0, -1, -2, and -3 as well as a summary of improved, no change, worsened, or died. Continuous change from baseline will be summarized descriptively along with two-sided 95% confidence interval and p-value from a paired t-test. Analysis of the endpoint will use the Attempted Implant set.

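### Eligible subjects all start in NYHA class I, so the planned t-interval and paired t-test on NYHA change sit on a boundary; report the proportion in class II or worse with an exact interval instead

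*SAP*

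**What the plan says.** Protocol 6.2.1 requires every inclusion criterion to be met before implantation, and criterion 2 is NYHA I. Protocol Table 15 describes class I as follows: "Patient is without limitations of physical activity". No class is better.

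SAP 7.9.2.5 plans three summaries of NYHA at 30 days and 6 months in the Attempted Implant set:
- counts and percentages by class;
- a categorical change table from 3 to -3, "as well as a summary of improved, no change, worsened, or died";
- a mean change: "Continuous change from baseline will be summarized descriptively along with two-sided 95% confidence interval and p-value from a paired t-test".

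The first two have no interval. For later visits, SAP 7.9.3 states: "Analysis for additional outcome measures 1-8 and 13 will follow the analysis methods defined for the same safety and efficacy endpoints at earlier timepoints". Item 6 on that list is annual NYHA change through 5 years. The initial analysis in SAP 7.8 takes place at 50 to 75 subjects: "Initial analyses will assess all safety and efficacy endpoints based on available data". Under SAP 7.4, unless otherwise specified, "all analyses will be based on available data and missing data will not be imputed".

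For device success, SAP 7.9.2.1 reports a percentage "with two-sided 95% exact binomial confidence interval", with subjects of known status as the denominator.

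**The concern.** If every eligible subject starts in class I, follow-up minus baseline can only be 0, 1, 2 or 3. A true mean change of zero then requires that nobody can worsen, so the paired t-test puts its null on the edge of the possible range. The t-interval assumes a roughly symmetric sampling distribution for the mean. With most changes at zero and a few at one, that assumption is poor.

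The study is meant to supply information for designing pivotal studies. In subjects who enter without symptoms, the NYHA figure of use to a planner is the share in class II or worse after TAVR, with an interval that can be trusted. The only interval the SAP plans for NYHA is the t-interval on the mean.

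**Working it through.** The plan gives no NYHA effect, SD or expected rate, so it has no figure of its own to reproduce. The worsening rate below is an assumption, shown over a range.

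**Inputs.** Baseline class I (Protocol 6.2.1). Up to 75 implanted subjects (SAP 5.1). Initial analysis from 50 subjects (SAP 7.8). Two-sided 95% interval (SAP 7.9.2.5). Assumed: everyone who worsens does so by one class, and all n subjects are assessed.

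**Formulas.** With k of n worsening, mean = k/n, SD = √[k(1 − k/n)/(n − 1)], and the interval is k/n ± t(0.975, n − 1) × SD/√n. At n=75 the t quantile is 1.9925. The comparator is the exact (Clopper-Pearson) interval for k/n.

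Example, k=3, n=75: SD = √(3 × 0.96/74) = 0.1973; SE = 0.1973/√75 = 0.0228; interval = 0.040 ± 0.0454 = −0.0054 to 0.0854.

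| Worsened of 75 | t-interval | t-test p | Exact interval |
|---|---|---|---|
| 0 | undefined (SD = 0) | undefined | 0 to 0.048 |
| 1 | −0.013 to 0.040 | 0.32 | 0.0003 to 0.072 |
| 2 | −0.011 to 0.064 | 0.16 | 0.003 to 0.093 |
| 3 | −0.005 to 0.085 | 0.083 | 0.008 to 0.1125 |
| 4 | 0.001 to 0.105 | 0.045 | 0.015 to 0.131 |
| 10 | 0.055 to 0.212 | 0.001 | 0.066 to 0.232 |

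For 0 worsened, the exact upper limit is 1 − 0.025^(1/75) = 4.8%; for 0 of 50 it is 1 − 0.025^(1/50) = 7.1%. At n=50 the lower t limit is again negative for 1 to 3 worsened.

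**Coverage.** For an assumed true rate π, sum the Binomial(n, π) probabilities of those k whose t-interval contains π. The k=0 case counts as a miss; a zero-width interval at 0 would miss as well.

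| True rate | t coverage, n=75 | P(nobody worsens), n=75 | t coverage, n=50 |
|---|---|---|---|
| 1% | 53% | 47% | 39% |
| 2% | 78% | 22% | 64% |
| 3% | 90% | 10% | 78% |
| 5% | 89% | 2% | 92% |
| 8% | 94% | 0.2% | 91% |
| 8.6% | 89% | 0.1% | 93% |
| 9% | 91% | 0.1% | 94% |
| 10% | 94% | <0.1% | 88% |
| 15% | 93% | <0.1% | 94% |
| 30% | 95% | <0.1% | 95% |

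In steps of 0.1 percentage points from 8% to 30%, coverage at n=75 runs from 89.1% (at 8.6%) to about 96%. It moves in jumps because k is a whole number: at 8.6%, the interval for k=3 ends at 0.0854 and just misses. The exact interval covers at least 95% at both sample sizes on a grid of the same step from 1% to 30%.

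**Source of the misses, n=75.** At 1%, 100 − 52.9 = 47.1 points are lost and 0.99^75 = 47.1% is the chance that nobody worsens, so that case accounts for essentially all of the loss. At 2% it accounts for 22.0 of 22.1 points, and at 3% for 10.2 of 10.4. At 5% the pattern differs. Of 11.0 points, 2.1 are the zero case, 8.4 are intervals that end below the true rate (k=1, upper limit 0.040) and 0.4 are intervals that start above it. Those misses mostly understate worsening.

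**The case against.** The strongest reply is that little depends on this analysis. The study has no formal hypotheses (SAP 7.5). NYHA change is an efficacy endpoint but not among the key ones in SAP 4, and nothing is decided on its p-value. For eligible subjects the worsened row of the planned table is the class II or worse group among those assessed, so the proportion can be read off and an interval computed from the published count. All of this stands, and it limits the weight of the point. It does not justify keeping an interval and a p-value that do not suit the data.

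Three stronger readings are tempting, and the documents do not support them.
- **Readers would be misled about half the time.** A reader might infer this from 53% coverage at a 1% rate. That figure comes almost wholly from the case where nobody worsens, and there the class counts and change table show the result correctly.
- **Deaths are lost from NYHA reporting.** They have no NYHA value and so are absent from the mean, but the SAP counts them in the categorical table. Their absence from a mean is ordinary available-case handling, and it does not by itself call for a composite of class II or worse with death. All-cause mortality has its own Kaplan-Meier analysis.
- **A test that can point only to worsening is itself a defect.** The direction follows from enrolling class I subjects. The replacement proportion cannot show improvement either.

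A milder reading also fails: that the t-interval becomes reliable once the rate reaches about 8%. At n=75 coverage is still 89% at 8.6% and 91% at 9%.

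**Conclusion.** The point holds as a modest analysis-choice defect. The mean NYHA change, its t-interval and its p-value do not suit an endpoint whose baseline is fixed at the best class. At n=75 the test is undefined with 0 worsened and the interval reaches impossible values with 1 to 3. Coverage falls below 95% at most of the assumed rates, severely at 1-2% and by up to about 6 points in places between 8% and 30%. What the plan lacks is a valid interval for a proportion it already tabulates.

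The coverage figures assume one-class worsening, complete assessment, and an undefined interval counted as a miss. The documents give no expected worsening rate. Protocol 6.16 allows up to 30 subjects with a positive exercise test, so neither a low nor a high rate can be taken for granted. The floor applies to eligible subjects; only someone treated in breach of criterion 2 could show improvement.

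**What to change.** In SAP 7.9.2.5, carried to item 6 of SAP 7.9.3:
- Delete the continuous NYHA change with its t-based interval and p-value.
- Keep the class counts and the categorical change table, including the row for deaths.
- Add, at each visit, the number and percentage in NYHA class II or worse among Attempted Implant subjects assessed at that visit, with the two-sided 95% exact binomial interval already used in SAP 7.9.2.1.
- Show beside it the number who have died and the number with missing NYHA, so the reader can see who is outside the denominator.

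The cost is one line of SAP wording and one extra interval per visit. No new data, visits or subjects are needed.
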